4 SELECTION AND ENROLLMENT OF PARTICIPANTS

Study Population: English-speaking (as discerned from the EMR) PLWD-Care partner dyads from the 4 participating clinics will be recruited. Dyads in the participating clinics will be identified in the following way:

- via warm handoff from a clinic provider to the ODC via the current standard of care for working with caregivers of PLWD regarding behavioral concerns, ODCs will be notified of the potential study participant by either of the two methods of ascertainment by the study RA. The ODC will then contact the care partner who is identified in the EMR as the responsible person or family member for the PLWD by telephone participation in the DICE program. We will also track the proportion of PLWD without a caregiver listed for study tracking.

Setting: Participants will be recruited from four primary care clinics in the Primary Care Network (total of 13) at University of California Davis. Clinics have been selected for the number of PLWD seen annually in each clinic. Below is preliminary information obtained on the potential subject population for the four study clinics from FY 1/1/2021-12/31/2021:

	Midtown	Elk Grove	ACC	FCC
>65 years old Dementia	63	67	66	76
Race/ethnicity				
White	40 (63.55)	35 (52.2%)	40 (63.5%)	27 (35.5%)
Black	11 (17.5%)	14 (20.9%)	11 (17.5%)	11 (14.5%)
Asian	8 (12.7%)	10 (14.9%)	8 (12.7%)	25 (32.9%)
Other	4 (6.4%)	8 (11.9%)	4 (6.3%)	
				13 (17.1%)

4.1 Inclusion Criteria

Participants must meet all inclusion criteria to participate in the study:

DICE participants

- 1) Person living with dementia (as defined by chart diagnosis) and their care partner
- 2) Care partner age >18 as defined in the EMR
- 3) Care partner English speaking

Historical controls

- 1) Person living with dementia (as defined by chart diagnosis)

4.2 Exclusion Criteria

- 1) Age of care partner <18 (this age group is rarely the responsible or legal party for PLWD)
- 2) Non-English speaking

4.3 Study Enrollment Procedures

PLWD-Care partner dyads from the 4 participating clinics will be recruited via warm handoff from a clinic provider. The ODC will then contact the care partner who is identified in the EMR as the responsible person or family member for the PLWD by telephone to discuss participation in the DICE Program. Participants will be recruited from four primary care clinics in the Primary Care Network (total of 13) at University of California Davis. Clinics have been selected for the number of PLWD seen annually by clinic social workers who are embedded in each clinic. As a minimal risk study embedded in primary care practices, we plan to obtain a waiver of informed consent for PLWD, care partners and clinic staff in order to reduce introduction of artificial care resources or biases wherever possible. There will be minimal PHI data collected.

5 STUDY INTERVENTIONS

5.1 Interventions, Administration, and Duration

This is a single group intervention. We have arranged with University of California Davis LVN supervisors to do a 6-hour training for all the LVNs on a single day. This will be a hybrid of in person (kick off session and ending brainstorming session) and watching the online modules together in a campus auditorium. ODCs will then use the approach in a “test” case in study months 2-3 during which they will engage in as needed coaching with a DICE trainer (a

geriatric psychiatrist and education specialist) to ensure they are using the approach with fidelity. Manualization and training with follow-up coaching have been shown to be effective implementation strategies that can enhance fidelity of implementation of an evidence-based program. Other clinic personnel (social workers and PCPs) will also receive the manual, an email overview of the study, and be invited to train using the website or at the on-site training. Following training and case consultation, the ODCs will then use the DICE Approach for any PLWD they encounter during the 6-month study period (months 4-9). Primary outcome metrics will be collected using the electronic medical record and by estimating time spent in the approach and strategies extracted from clinic notes.

As part of the DICE program, the ODC will meet with the PLWD-Care partner dyad by phone to determine if any BPSD are present. If no BPSD are currently present, the ODC will educate the care partner about DICE, including minimizing risk factors to prevent behaviors, and plan to continue monitoring (26) for BPSD during the 6-month study period. If BPSD are occurring, then the “Describe” and “Investigate” Steps of DICE will be triggered.

Each step of DICE will be documented by the ODC in their clinic note within the EMR as is part of usual practice. In the “Describe” step, the ODC will obtain an accurate characterization of the behavior and the context in which it occurs as well as quantify the frequency and severity of the most troublesome behavior (as defined by the care partner) using the one-item question we have used in prior trainings (16, 17): “Please rate from 0 to 4 the severity and frequency of the behavior (0=none or never; 1=mild and/or occasionally; 2=moderate and/or sometimes; 3=severe and/or frequently; and 4=very severe and/or daily). If the severity and frequency are different, pick the higher score (e.g. a behavior that is daily but mild should be scored as a 4)”. In the “Investigate” step, the ODC will identify possible underlying and modifiable causes of the behavior.

With information obtained in the “Describe” and “Investigate” steps, the ODC will work with the care partner to create and implement a treatment plan to manage BPSD. The ODC will brainstorm with the care partner (e.g. what are activities the PLWD enjoys) and instruct the care partner in behavioral and environmental strategies. These approaches could include enhancing effective communication with the PLWD, creating meaningful activities, dealing with environmental challenges including ensuring safety, and simplifying tasks and creating structured routines. The ODC will also consult with other relevant clinic personnel on the Create treatment plan as needed; for example, a plan may involve having the provider assess and manage infection, constipation or pain. From prior experience with DICE, these first three steps (Describe, Investigate, Create) can be accomplished in 30 minutes.

Following the “Create” step, and in a 2-week follow-up contact by telephone, the ODC will engage in the “Evaluate” step with the care partner, during which the ODC will determine if recommended strategies were used and their effectiveness. Effectiveness will be measured by repeating the frequency/severity question asked of the care partner in Describe so that the impact of the strategy can be assessed quantitatively comparing the pre- and post-strategy scores at 2 weeks’ time; any downward movement of the score will be categorized as effective. If the DICE generated strategies were effective, the ODC will monitor and surveil for BPSD with monthly contact. If the DICE generated strategies were not effective, the ODC will

problem-solve with the care partner and other team members to determine if a) strategies were used and if so correctly; or b) if strategies are not effective and additional “Create” recommendations are needed. Additionally, the DICE trainer (MB) will be available to ODC for coaching regarding the DICE Approach as needed during the study period.

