6 STUDY PROCEDURES

6.1 Schedule of Evaluations

Assessment	Screening:	Baseline, Enrollment, Visit 1 (Day 0)	Followup, Visit 2 (Day 14)	Followup Visit 3 (Day44)	Followup Visit 4 (Day 74)	Followup Visit 5 (Day 104)	Followup Visit 6 (Day 134)	Followup Visit 7 (Day 164)
Verification of dementia diagnosis and eligibility via inclusion/exclusion criteria	X							
Demographics	X							X
Current Medications	X	X	X	X	X	X	X	X
Hospitalizations								X
Nursing Home Placement								X
ED Visits								X
Adverse Events		X	X	X	X	X	X	X

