9 STATISTICAL CONSIDERATIONS

9.0 General Design Issues

The overarching goal of this proposal is to refine and pilot the application of DICE in primary care clinics by: (a) leveraging existing clinic staff to deliver DICE; and (b) using electronic resources to identify and recruit PLWD-care partner dyads based on clinically relevant and minimum inclusion/exclusion criteria. We maximize a pragmatic approach and minimize a separate study infrastructure to evaluate feasibility and acceptability in order to prepare for a larger embedded pragmatic trial (ePCT). Licensed practical nurses embedded in four primary care practices at University of California Davis (UCD), whom we will refer to as “Onsite DICE Coordinators” (ODC), will coordinate behavioral management using DICE with care partner-PLWD dyads and other clinic providers. We will accomplish this goal through the following specific aims:

Aim 1. To assess the feasibility and acceptability of the ePCT protocolized version of DICE that will guide the subsequent evaluation of the effectiveness of the intervention in a full-scale ePCT. DICE will be implemented in four large primary care clinics within the UCD Health System over a 6-month period (n=100 PLWD-care partner dyads; 25 dyads per site, allowing comparison of implementation and outcomes by site characteristics). Feasibility measures will include: 1) rate of subject enrollment (PLWD-care partner dyads); 2) number of contacts between ODCs and dyads; and 3) time requirements for ODCs implementing DICE. Acceptability will be measured by the acceptance rates of the ODC’s recommendations of strategies for BPSD (generated by use of DICE) among dyads, as well as other providers within the primary care practice. Exit interviews of participants (ODCs, other providers and care partners) will be conducted to further deepen the knowledge of intervention acceptability and implementation challenges.

Aim 2. To determine the feasibility of ascertaining and analyzing the primary (psychotropic medication use) and secondary clinical outcomes (hospitalizations, ED visits and nursing home placement of PLWDs) from the existing health system-wide electronic medical record (EMR) which will subsequently be used in a full-scale effectiveness ePCT. Clinical outcomes for PLWD participants will be measured after the 6-month DICE implementation period using the EMR and

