9.1 Sample Size and Randomization

We will examine data across 4 clinics in order to assess the feasibility of a multi-site study. We selected 25 dyads per clinic as our sample size (primary study sample- total n=100 PLWD), and their caregiver (n=100) in order to have the ability to examine feasibility measures within clinic as well as across clinic with some accuracy. For example, the degree of accuracy around an enrollment rate of 75% overall is 18% (width of the 95% confidence interval), allowing us a tighter margin of error overall. Within clinic, accuracy is larger (width of 95% confidence interval 36%), suggesting more uncertainty, but allowing us to examine clinic-specific enrollment to ensure that there is consistency across clinics.

To determine the feasibility of ascertaining and analyzing the primary (psychotropic medication use) and secondary clinical outcomes (hospitalizations, ED visits and nursing home placement of PLWDs) from the existing health system-wide electronic medical record (EMR) participants (the primary study sample of PLWD n=100) will be measured after the 6-month DICE implementation period using the EMR and compared to corresponding outcomes for the four participating clinics in the 6 months prior to the intervention (historical controls n=100); all PLWD in the four participating clinics), (N=300).

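### No enrollment window is defined: if entry and follow-up share months 4-9, participants average about half the exposure of the 6-month historical comparison, and the count analysis has no person-time

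*Combined protocol and SAP*

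**What the plan says.** **Entry and delivery.** Section 5.1 has the coordinators (ODCs) "use the DICE Approach for any PLWD they encounter during the 6-month study period (months 4-9"; the Précis and section 3 say the same. Section 9.0 adds that "DICE will be implemented in four large primary care clinics within the UCD Health System over a 6-month period". Entry is rolling: in section 4.3, "PLWD-Care partner dyads from the 4 participating clinics will be recruited via warm handoff from a clinic provider". For a dyad with no current symptoms, section 5.1 has the coordinator "plan to continue monitoring (26) for BPSD during the 6-month study period".

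**Schedule.** The table in section 6.1 runs from Day 0 to "Followup Visit 7 (Day 164". Medications are marked at every visit. Hospitalizations, ED visits and nursing home placement are marked only at the last one.

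**Size.** Section 9.1 states "We selected 25 dyads per clinic as our sample size (primary study sample- total n=100 PLWD" and justifies it by the width of a confidence interval around the enrollment rate.

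**Comparison.** Sections 9.0 and 9.4 compare participants in the intervention period with PLWD in the four clinics over the 6 months before it. Section 9.5 names a logit mixed model for psychotropic use (yes/no), then treats hospitalization and ED counts and a binary nursing home measure in a similar way. It mentions no time at risk.

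**The concern.** A dyad that enters late in months 4-9 has little follow-up left inside them. With no separate accrual period, time under observation depends on entry date, while the historical side has a fixed 6 months.

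Three results are at stake:
- The utilization comparison could show an apparent benefit produced by exposure alone.
- The pre-post change in psychotropic use feeds one of the two criteria in section 9.5 for going on to the full trial.
- The number of contacts per dyad, an Aim 1 feasibility measure, would partly measure how early a dyad entered, and so mislead workload planning for the full trial.

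**Working it through.** **1. The plan's own figures.** At an enrollment rate of 75%, the exact (Clopper-Pearson) 95% interval is 17.8% wide for 75/100 and 35.8% wide for 19/25. These reproduce the 18% and 36% in section 9.1. Neither figure uses follow-up.

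**2. Inputs.**
- Period: 6 months (section 5.1), taken as 182.5 days; 180-184 depending on the calendar.
- Visits: Days 0, 14, 44, 74, 104, 134, 164 (section 6.1).
- Pool: the row ">65 years old Dementia" in section 4, 63 + 67 + 66 + 76 = 272 in one year.
- Enrollment rate: 75% (section 9.1).
- Assumptions, not in the documents: even entry over the period, follow-up ending at month 9, and the annual pool spread evenly.

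**3. Entry that leaves room for Day 164.** 182.5 - 164 = 18.5 days (16-20 for periods of 180-184 days).

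**4. Share of dyads reaching day d.** Formula: (182.5 - d)/182.5.

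| Day | Share |
|---|---|
| 14 | 92% |
| 44 | 76% |
| 74 | 59% |
| 104 | 43% |
| 134 | 27% |
| 164 | 10% (8.9-10.9% for 180-184 days) |

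Scheduled contacts that fit, per dyad: 1 + 0.92 + 0.76 + 0.59 + 0.43 + 0.27 + 0.10 = about 4.1 of 7.

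**5. Exposure.** Mean time from entry to month 9 is 182.5/2 = 91.25 days. Expected count = rate x time, so with equal true rates the ratio of participant to historical mean counts is 91.25/182.5 = 0.50.

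**6. The other way to count.** If all of months 4-9 is counted for everyone, the windows are equal, but on average 182.5 - 91.25 = 91.25 days, half the time, precedes the dyad's entry. Any effect is then diluted. The plan does not say which window applies.

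**7. Can 100 be enrolled?** Over six months, 272 x 182.5/365 = 136 PLWD, and 136 x 0.75 = 102 dyads. In 18.5 days, 272 x 18.5/365 = 13.8, and 13.8 x 0.75 = about 10 dyads. The target therefore fits accrual over the full six months, which is the case that truncates follow-up.

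**8. Outcomes without a computed size.** Nursing home placement as a yes/no event has less time to occur in a shorter window. Psychotropic use also depends on window length, but less so where it is continuing use. The documents give no rates from which to size either effect.

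**The case against.** A reader might infer that the trial cannot be delivered because only about 19 days remain for enrollment. The documents do not support that. They nowhere require Day 164 to fall inside months 4-9, and the monitoring wording could be read as six months per dyad. Section 6.2.3 calls visits flexible and gives their timing as a general pattern. On the plan's own pool, 100 dyads are attainable over six months.

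A reader might also infer that Aim 2 data are lost for dyads that miss Visit 7, or that section 9.1 overstates the sample. Neither follows. Clinical outcomes are read from a shared EMR after the implementation period (sections 9.0, 9.4), and section 8 continues to follow PLWD who leave routine care. Section 9.1 sizes the enrollment-rate interval and promises no number of Day-164 completers. Section 9.5 concedes limited power. Restricting Aim 2 to completers would discard usable data.

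Early, concentrated entry is not excluded either. Electronic resources are to be used to identify dyads, and 25 first visits of 30 minutes come to 12.5 hours per coordinator. But no section plans it. It would need about 134 invitations (100/0.75), 49% of the annual pool, within 18.5 days.

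Finally, section 9.4 speaks of rates, which might imply person-time. Section 9.5, where the analysis is specified, gives only counts.

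These points remove the claim of infeasibility. They do not settle the exposure question: flexible visits do not define an accrual window, and complete EMR capture does not equalize time at risk. The nursing home check in section 9.4 also needs a care partner's report, and that item is scheduled only at the last visit, although a flexible final visit could supply it earlier.

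**Conclusion.** The plan leaves the enrollment window undefined and, on its natural reading, runs entry and follow-up in the same six months. Under even entry with follow-up ending at month 9, about 10 of 100 dyads would have the full schedule, and mean exposure would be about 91 days against a historical 6 months. If only post-entry time is counted, equal hospitalization or ED rates would appear as roughly a halving. Front-loaded entry, or follow-up past month 9, would shrink the problem; the documents specify neither. The binary outcomes and mean contacts are affected in the same direction. This is a correctable flaw in the Aim 2 comparison and in one Aim 1 summary, and it does not show that 100 dyads are out of reach.

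**What to change.** **Preferred.**
- In sections 3, 5.1 and 9.1, state the enrollment window separately from follow-up.
- In sections 9.4 and 9.5, define each participant's outcome window from their own Day 0, with a fixed length equal to the historical control window.
- Set the EMR extract after the last dyad completes that window.

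**If the study must end at month 9.**
- Keep all 100 PLWD in Aim 2.
- Add a log person-time offset to the count models.
- Use a time-at-risk or equal-window definition for psychotropic use and nursing home placement.
- Summarize contacts per month of follow-up.
- State the expected number with full follow-up (about 10 under even entry).

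**Cost.** Protocol wording, plus an extract up to about 5-6 months later if entry runs to month 9: 182.5 + 164 = 346.5 days, about 11.4 months from first entry, or 12 months with a full 6-month outcome window. Care-partner reports of nursing home placement would need to be obtained over the same time. The alternative costs a smaller stated number with complete follow-up. Neither needs more patients.

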5.2 Handling of Study Interventions

See above.

5.3 Concomitant Interventions

Not applicable.

5.4 Adherence Assessment

Rather than adherence, in this pilot study, we will be examining feasibility and acceptability. Feasibility measures will include: 1) rate of enrollment of PLWD-care partner dyads; 2) number of contacts between ODCs and dyads; and 3) time requirements for ODCs implementing DICE (as estimated by the ODCs and corroborated by clinic notes).

Acceptability will be measured by the acceptance rates of the ODC’s recommendations of strategies for BPSD (generated by use of DICE) among dyads, as well as by other providers within the primary care practice.

6 STUDY PROCEDURES

6.1 Schedule of Evaluations

Assessment	Screening:	Baseline, Enrollment, Visit 1 (Day 0)	Followup, Visit 2 (Day 14)	Followup Visit 3 (Day44)	Followup Visit 4 (Day 74)	Followup Visit 5 (Day 104)	Followup Visit 6 (Day 134)	Followup Visit 7 (Day 164)
Verification of dementia diagnosis and eligibility via inclusion/exclusion criteria	X							
Demographics	X							X
Current Medications	X	X	X	X	X	X	X	X
Hospitalizations								X
Nursing Home Placement								X
ED Visits								X
Adverse Events		X	X	X	X	X	X	X

6.2 Description of Evaluations

Please refer to Section 3.

6.2.1 Screening Evaluation

Consenting Procedure

Not applicable. A waiver of informed consent will be sought as DICE will be part of any contact by the ODC with care partners about behavioral concerns in the PLWD. A waiver of information consent will also be requested for access to the EMR for the historical controls.

6.2.2 Enrollment, Baseline, and/or Randomization

Enrollment

Enrollment will follow identification and meeting of inclusion and exclusion criteria.

6.2.3 Follow-up Visits

Visits will be flexible and tailored to the needs of each care partner and PLWD as part of usual care. However, in general, Visit 1 will consist of meeting with the care partner over the phone to determine if any behavioral or psychological symptoms of dementia (BPSD) are present. If none are present, the ODC will educate the care partner about BPSD and the DICE Approach and create a plan for monitoring during the 6-month study period. If BPSD are present, the “Describe” and Investigate” steps of the DICE intervention will be triggered. Using this information during the same visit, the ODC will work with the care partner to create and implement a treatment plan. This visit will be accomplished in 30 minutes. Visit 2 will occur approximately 2 weeks after the first visit. The ODC will engage in the “Evaluate” step to determine if the treatment plan was implemented and its effectiveness. If effective, the ODC will monitor and surveil for BPSD with monthly contact. If not effective, the ODC will work with the care partner to create additional treatment strategies and then follow up at intervals between 2 weeks and 1 month as needed.

6.2.4 Completion/Final Evaluation

At the final visit, an evaluation of the current effectiveness of DICE strategies will be performed. Exit interviews of participants (ODCs, other providers and care partners) will be conducted to further deepen the knowledge of intervention acceptability and implementation challenges. We will seek a waiver of informed consent for these interviews which will be conducted by study team members.

7 SAFETY ASSESSMENTS

The anticipated risks are very minimal given that this is a non-pharmacologic intervention being implemented to enhance usual care.

7.1 Specification of Safety Parameters

NA

7.2 Methods and Timing for Assessing, Recording, and Analyzing Safety Parameters

NA

7.3 Adverse Events and Serious Adverse Events

Adverse Event (AE): Any untoward or unfavorable medical occurrence in a clinical research study participant, including any abnormal sign (e.g. abnormal physical exam or laboratory finding), symptom, or disease, temporally associated with the participants' involvement in the research, whether or not considered related to participation in the research.

Serious Adverse Event (SAE): Any adverse event that:

- Results in death
- Is life threatening, or places the participant at immediate risk of death from the event as it occurred
- Causes persistent or significant disability or incapacity
- Results in congenital anomalies or birth defects
- Is another condition which investigators judge to represent significant hazards

No AE's or SAE's are expected based upon the study intervention. Hospitalizations and ED visits are secondary outcomes in the study and not considered adverse events. However, we will collect data on such events from the medical chart and caregiver report during visits and report them as needed.

